11.7 Safety Assessments

11.7.1 Adverse Events

Adverse events will be classified into standard terminology using the Medical Dictionary for Regulatory Activities (MedDRA). Adverse events will be listed by reported verbatim term and MedDRA-preferred term, start and stop date and time, study day, duration, severity, relationship to study drug, and seriousness. Additionally, data may be grouped for analysis by different levels of the MedDRA hierarchy. The incidence of AEs, the incidence of treatment-related AEs, and the severity of AEs will be tabulated by cohort.

The number and percentage of patients with SAEs and treatment-related SAEs and patients who withdraw due to an AE will be tabulated by cohort.

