Study Design	
This is a Phase 2a, multi-center, open-label study, conducted in two cohorts of patients diagnosed with acute liver failure/severe acute liver injury (ALF/ALI) who meet inclusion/exclusion criteria. Cohort 1 is defined as patients with ALF/ALI with minimal renal dysfunction at the time of enrollment (defined as a serum creatinine ≤ 1.5 mg/dL and mean arterial pressure of >65 mm Hg). Cohort 2 is defined as patients with ALF/ALI with compromised renal function (defined as a serum creatinine >1.5 mg/dL and <10 mg/dL with mean arterial pressure of >65 mm Hg).
 
Informed consent will be obtained from the patient and/or patient's legally authorized representative (LAR) or family member as defined in 21CFR50.3(m). All patients will receive medical care for acute liver failure/severe acute liver injury according to the institution's standards of care. Standard of care may include, but is not limited to, administration of N-acetylcysteine and consideration for orthotopic liver transplantation.
 
Up to 36 evaluable patients will be enrolled. An evaluable patient is one who has received an infusion of OCR-002 for at least 72 hours. It is expected that not every enrolled patient will be treated for at least 72 hours due to transplant, death or early hospital discharge. Due to this, we anticipate 25% of the enrolled population will fail to reach evaluable status. Therefore, we plan to enroll up to 50 patients in order

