7.4 Timing of Dosing and Administration of OCR-002 Infusion

Study drug dosing should be initiated as soon as possible upon admission to the registry but only after obtaining informed consent, ensuring all eligibility criteria are confirmed to be met and completing the initial baseline evaluation period. The window between obtaining informed consent and initiation of OCR-002 infusion may be up to 32 hrs in order to complete any pre-study drug initiation requirements and/or to provide a time frame for study drug administration. Each cohort will receive a continuous infusion of OCR-002 for up to 5 days (between 0 to 120 hours).

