8.4 Follow Up or Early Termination

A safety follow-up visit will be performed approximately 30 days from Treatment Day 1-T0 (start of infusion) for all patients who completed the study drug infusion period or who discontinued the study drug infusions but remain in the study.

- Collection of blood for hematology, coagulation, clinical chemistry, ammonia;
- Vital signs and abbreviated physical exam;
- Neurological battery, including:
 - Glasgow Coma Scale;
 - West-Haven Scale; and
 - O-Log Scale;
- Review and reporting of Serious Adverse Events (SAEs).*

* Non-serious adverse events (AEs) and Serious Adverse Events (SAEs) are collected from Treatment Day 1 at T0 through 24 hours Following Completion of the Last

Infusion. After the 24 hours Following the Completion of the Last Infusion time point, only SAEs are collected through the Day 30 post treatment period.

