9 SAFETY ASSESSMENTS

Details for safety assessments will be recorded in both the CRF and the patient's source documents. During the study, the Investigator or study site personnel will be responsible for querying and recording AEs and SAEs. Adverse events will be recorded from the start of the initial administration of OCR-002 (Treatment Day 1-T0) until 24 hours Following the Completion of the Last Infusion. Serious adverse events will be recorded from Treatment Day 1-T0 through the remainder of the study period. AEs will be evaluated by the Investigator for severity, seriousness, and relationship to study drug as outlined below. Untoward medical events which occur *after* signature of the informed consent *but before* study drug administration will be recorded as medical history.

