9.3 Reporting Adverse Events from Participating Clinical Sites

Safety assessments will consist of monitoring and reporting all adverse events from the start of the initial study drug infusion through 24 hours following the final infusion of study drug (typically Day 5) or for 24 hours following the final infusion of study drug for those patients who do not complete the entire course of study drug administration. Adverse events that do not meet the definition of “serious” or “suspected adverse reactions” will be reviewed periodically throughout the trial to identify any previously unidentified trends or other safety issues.

In order to ensure prompt reporting of adverse events, we require that all non-serious adverse events must be entered into the WebDCU™ database system within 5 working days following the completion of Treatment Day 1-T0 through 24 hours Following the Completion of the Last Infusion study phases (e.g., Day 1 phase is Tuesday, 02JAN2012; any AEs occurring in that phase must be entered into the WebDCU™ database system no later than Monday, 09JAN2012).

9.4 Reporting Serious Adverse Events and Suspected Adverse Reactions from Participating Clinical Sites

With regard to serious adverse events and suspected adverse reactions, both expected and unexpected and regardless of whether the SAE/SARs are considered related to the study drug and/or the disease, they will be followed in a rigorous review process through the entire trial period. Clinical performance sites are instructed to report all fatal events, unanticipated problems and other serious adverse events and suspected adverse reactions in the WebDCU™ database system **within 24 hours of first knowledge of the event**. Additionally, all current study data for that particular patient must be entered to allow for timely review by the Internal Medical Monitor (IMM) and the independent external Medical Safety Monitor (MSM). In adjudicating cases at UT Southwestern, an alternate IMM will serve in place of the IMM.

The clinical site Investigator, on the basis of his or her clinical judgment and the following definitions, determines the relationship of the adverse event to the protocol intervention as one of the following:

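### Crude incidence of non-serious AEs depends on how long and why each patient was infused, because the AE window follows the infusion and no time-at-risk summary is planned

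*Combined protocol and SAP*

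**What the plan says.** **Collection.** Section 9 has AEs "recorded from the start of the initial administration of OCR-002 (Treatment Day 1-T0) until 24 hours Following the Completion of the Last Infusion". Section 9.3 applies the same rule to early stoppers: AEs are monitored "for 24 hours following the final infusion of study drug for those patients who do not complete the entire course". After that point, Section 8.4 states, "only SAEs are collected through the Day 30 post treatment period".

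**Infusion length.** Section 7.4: "Each cohort will receive a continuous infusion of OCR-002 for up to 5 days (between 0 to 120 hours". The synopsis adds that "we anticipate 25% of the enrolled population will fail to reach evaluable status", where evaluable means at least 72 h of drug, and names transplant, death and early discharge as the expected causes. Section 6.3.4 also lists toxicity among the reasons for discontinuing.

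**Analysis.** Section 11.7.1: "The incidence of AEs, the incidence of treatment-related AEs, and the severity of AEs will be tabulated by cohort". Section 11.6 gives the form of categorical summaries: number and proportion of patients, overall and by cohort. Section 11.4 makes the per-protocol set (at least 72 h of drug) primary for all outcomes and uses ITT for sensitivity. It defines a safety population but assigns it no analysis. The memorandum at the end of the file confirms that there is no separate SAP, so Section 11 is the whole plan. It contains no person-time rate, time-to-event summary or common AE window.

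**The concern.** A proportion of patients with an AE compares like with like only if patients are watched for similar periods. Here the period is set by the infusion, and the infusion can end for reasons tied to prognosis or tolerability. Two cohorts with the same underlying AE rate can show different proportions, and two with different rates can show the same one.

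What is at stake is how the primary-objective tables are read for non-serious AEs. Several effects listed in Section 9.1.2 as possibly drug-associated, such as dizziness, nausea, headache and chills, will often be non-serious. The study is descriptive, so these proportions are the result and no model follows to correct them.

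**Working it through.** **The plan's own figure.** The synopsis states "Up to 36 evaluable patients will be enrolled" and allows for 25% not reaching 72 h. 36 / (1 − 0.25) = 48, which fits the stated enrolment of up to 50. Early stopping is thus built into the plan.

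**Window.** AE window = infusion hours + 24 (Sections 7.4 and 9).

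| Infusion (h) | 24 | 48 | 72 | 96 | 120 |
|---|---|---|---|---|---|
| AE window (h) | 48 | 72 | 96 | 120 | 144 |
| Share of full window | 33% | 50% | 67% | 83% | 100% |

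**Effect on a crude proportion.** The documents give no AE rate, so I assume a constant hazard and a full-course (144 h) incidence p of 20, 40, 60 or 80%. With stopping unrelated to AEs, the expected proportion over a window of t hours is F(t) = 1 − (1 − p)^(t/144). Example: p = 40%, t = 48 gives 1 − 0.6^(1/3) = 15.7%.

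| p | F(48) | F(72) | F(96) | F(120) | F(144) |
|---|---|---|---|---|---|
| 20% | 7.2 | 10.6 | 13.8 | 17.0 | 20.0 |
| 40% | 15.7 | 22.5 | 28.9 | 34.7 | 40.0 |
| 60% | 26.3 | 36.8 | 45.7 | 53.4 | 60.0 |
| 80% | 41.5 | 55.3 | 65.8 | 73.8 | 80.0 |

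**Gap between two cohorts with the same hazard.** Assume that 10% of one and 40% of the other stop at s hours, and that all others complete 120 h. The two shares average the documented 25%, but the split is my assumption. Gap = (0.40 − 0.10) × [F(144) − F(s + 24)].

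| p | s = 24 h | s = 48 h | s = 72 h (all per protocol) |
|---|---|---|---|
| 20% | 3.8 | 2.8 | 1.9 |
| 40% | 7.3 | 5.2 | 3.3 |
| 60% | 10.1 | 7.0 | 4.3 |
| 80% | 11.5 | 7.4 | 4.3 |

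In ITT or safety-population tables the gap is 2.8 to 11.5 points. In the per-protocol set, where the shortest window is 96 h, the same split gives 1.9 to 4.3 points.

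**Masking.** A patient with 1.5 times the AE rate who stops at 72 h has 1.5 × 96 = 144 full-rate hours, and so the same expected proportion as a full-course patient.

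**Per-protocol against ITT.** If 25% stop at 24 h and the rest complete, then at p = 40% the completers show 40.0% and all treated patients show 0.75 × 40.0 + 0.25 × 15.7 = 33.9%, with no difference in hazard.

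**When the direction reverses.** A patient stopped for an AE already counts as having one. Let q be the share of 24 h stoppers, among those who would otherwise have no recorded AE, who stop because of an AE. Their incidence equals the full-course figure when q = (p − F(48)) / (1 − F(48)). That is 0.289 at p = 40% and 0.457 at p = 60%. Above that share, early stoppers look less safe in the any-AE row.

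**The case against.** **Direction.** A reader might infer that early stopping always makes a group look safer, and so biases the renal comparison towards no difference. The documents do not support that. A toxicity stop adds an event to the any-AE row and to its own preferred term. Early discharge could shorten windows in the healthier cohort just as other causes could in the sicker one, and no document gives stopping by cohort. For AE terms other than the one that led to stopping, a shorter window still lowers the count.

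**Serious events.** SAEs are collected to Day 30 whatever the infusion length, and the Section 9.7.1 criteria rest on SAEs. This stands: the point is confined to non-serious AEs. Section 9.4 also describes suspected adverse reactions as collected to Day 30, whereas Section 8.4 restricts that period to SAEs. If Section 9.4 governs, the treatment-related rows are less affected.

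**Primary table.** The per-protocol set excludes anyone stopped before 72 h. This stands and shrinks the effect there to the 96 to 144 h spread. The full spread remains in the ITT sensitivity analysis and in the quarterly safety reports on all enrolled patients (Section 11.5).

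**Tolerability is shown elsewhere.** Section 11.7.1 already tabulates withdrawals due to an AE by cohort, and Section 11.5 reports reasons for early withdrawal. These help the reader but do not put the incidence columns on a common footing.

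**Noise.** With 18 patients and 40% incidence, the 95% half-width is 1.96 × √(0.4 × 0.6 / 18), about 23 points, well above a 7-point gap. That limits what any comparison can show, but a confidence interval does not cover a systematic difference in observation time.

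**Person-time has its own bias.** Section 3.3.2 says adverse effects may be related to rate and peak concentration, and Dose Levels 2 and 3 change rate within 24 h, so a constant hazard is doubtful. Suppose 0.4 events per patient all fall in the first 24 h. A 36 h window (1.5 days) gives 0.4 / 1.5 = 26.7 per 100 patient-days and a 144 h window (6 days) gives 6.7, although the crude proportions agree. This stands, and is why a person-time rate alone is not the remedy.

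**Conclusion.** The point holds as a limit on interpretation, not as a demonstrated bias in a known direction. The non-serious AE window follows each patient's infusion, the planned summary is a plain proportion, and nothing in Section 11 accounts for time observed. The illustrated size is about 3 to 12 points in tables of all treated patients and about 2 to 4 points per protocol. Both ranges rest on assumptions the documents do not supply: a constant hazard common to both cohorts, full-course incidences of 20 to 80%, stopping unrelated to AEs, and a 10% versus 40% split. SAE tables are not affected by infusion length. The trial is not invalidated, but its non-serious AE tables need observation time beside them to be read properly.

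**What to change.** In Section 11.7.1, keep the proportions and name the population for each AE table. Then add, by cohort:

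1. AE-window length (summary statistics) and reason for stopping infusion.
2. AE incidence within a common window: T0 to 96 h for the per-protocol set. By design, every patient in that set is observed to 96 h unless death or withdrawal of consent intervenes.
3. Time to first AE for all treated patients, censored at the end of each patient's AE window, with death as a competing event (Aalen-Johansen cumulative incidence).
4. As a supplement, first events per 100 patient-days at risk with exact Poisson 95% confidence intervals, and a note that the rate assumes a roughly constant hazard.

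Also reconcile Sections 8.4 and 9.4 on how long non-serious suspected adverse reactions are collected, so that the window for the treatment-related rows is defined.

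Cost: a few table columns and one added summary. Infusion start and stop times (Section 7.5) and AE start and stop times (Section 11.7.1) are already recorded. Extending non-serious AE collection to a fixed 144 h for everyone is optional. It would need an amendment and extra data entry for early stoppers, and this fix does not depend on it.

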11.7.2 Clinical Laboratory Tests

Clinical laboratory test parameters will be listed for individual patients. Baseline for clinical laboratory parameters will be defined as the last evaluation before the start of the initial dosing with study drug. Summary statistics, including mean absolute change from baseline, will be calculated for each parameter and summarized.

11.7.3 Vital Signs

Vital signs results (systolic and diastolic blood pressure, pulse rate and body temperature) will be listed for individual patients. Each vital sign measure will be tabulated by evaluation time point. Baseline for vital signs measurements will be defined as the last evaluation before the beginning of the first OCR-002 infusion (which will generally be Baseline, pre-dose). Summary statistics, including mean absolute change from baseline, will be determined and tabulated for each measure.

11.7.4 Electrocardiograms

Means of the ECG intervals/durations will be listed for individual patients. Summary statistics, including mean absolute change from baseline, will be determined and tabulated by cohort.

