3.3.2 Rationale for Dose Selection

Ocera Therapeutics, Inc. (Durham, NC) has conducted two clinical trials evaluating safety, tolerability and pharmacokinetics in healthy volunteers (n=48) and stable cirrhotic patients (n=43).

Clinical study OCR-002 HE201 was designed as a randomized, placebo-controlled, dose-ranging study, evaluating doses (i.v. infusion) of 1, 3, 10, 20 and 30g given over 4h, and 30, 40 and 60g given over 24h. Following a single ascending dose phase, a multiple ascending dose phase (5d of consecutive administration) for doses of 1, 3, 10 and 20g given over 4h was assessed. The key findings in this study included:

There were no deaths, SAE or AE discontinuations in the study.

A dose related increase in the incidence and severity of adverse events was observed.

Commonly occurring adverse events that appeared to be related to dose included dizziness, somnolence, headache, nausea/vomiting and tinnitus.

There was no evidence to suggest that AEs increased or new AEs occur with multiple dosing.

With respect to blood pressure, there were no apparent trends from placebo with respect to mean changes from baseline; however at dose levels $\geq 20\text{g}/4\text{h}$, several patients experienced clinically significant orthostatic hypotension.

There appeared to be a dose and exposure related increase in mean heart rate starting at a dose level of $10\text{g}/4\text{h}$ and higher. These effects also persisted for longer periods in the higher dose groups.

20g administered over 4 h was the maximum tolerated dose (MTD), however, doses of $10\text{g}/4\text{h}$ and below were well tolerated.

24h Holter monitor recording identified a dose-related increase in heart rate accompanied by modest effects on ventricular repolarization as measured by QT. These effects should be interpreted with caution in light of the small sample size and higher heart rates observed in this study.

There were no clinically significant abnormal laboratory parameters and no patient had any clinically significant changes in physical examination findings or mean

change in body weight between baseline and follow up.

Doses higher than 10g/4h are associated with adverse effects that may be rate and C_{max} related and are likely associated with the non-linear pharmacokinetic profile of phenylacetate above 10 g.

A slower infusion rate (24hr-infusion) avoids C_{max} related adverse effects while providing similar excretion of PAGN.

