6.2.2 Exclusion Criteria

1. History of chronic liver disease.
2. Signs of overt cerebral herniation, or uncontrolled intracranial hypertension by ICP monitoring (if applicable).
3. Evidence of Wilson's disease, alcoholic hepatitis, biliary obstruction, ischemic hepatitis, severe acute renal tubular necrosis (ATN) due to shock, or any patient with ongoing hypotension.
4. Significant gastrointestinal bleeding (coffee grounds per nasogastric tube and/or melena).
5. Hemodynamic instability, defined by a mean arterial pressure of $<$ 65 mmHg.
6. Cardiopulmonary complications such as pulmonary edema, aspiration pneumonia, heart failure.
7. QT interval of $>$ 500 msec at baseline ECG.
8. Pregnancy.
9. History of malignancy that has not been cured or any cancer in remission for less than 1 year. Non-melanoma skin cancers do not preclude participation in the trial.

10. Concomitant administration of drugs known to interfere with renal excretion of phenylacetylglutamine or those medications that may induce hyperammonemia such as haloperidol, valproic acid and systemic corticosteroids (prohibited during the study). Alternative ammonia modifying agents such as lactulose and rifaximin are not considered standard of care and are prohibited during the study period.
11. Any other health condition that would preclude participation in the study in the judgment of the principal investigator.

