6.3.4 Discontinuation of Study Treatment

An Investigator may discontinue a patient's treatment at any time to protect the patient's safety. Reasons that patients may have treatment discontinued include, but are not limited to the following:

- Prolongation of Qt/Qt_c interval of >60 msec over baseline or a Qt/Qt_c interval above 500 msec;
- Evidence of torsades de pointe phenomenon;
- Grade 3 or higher CTCAE toxicity not attributed to acute liver failure in the opinion of the investigator;
- Neutropenia with absolute neutrophil count <500/cumm or platelet count <20,000/cumm, or an increase in serum Cr to a value of >10mg/dL;
- Liver transplantation during the study treatment;
- Withdrawal of informed consent by the patient or patient's legally authorized representative or family member;
- In the case of interruption of infusion for any reason, the study drug will not be restarted if more than 2 hours has elapsed;
- Evidence of shock; and
- Evidence of kidney injury related to study drug will invoke consideration of discontinuation of the study drug.

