9.8 Safety Assessments

Laboratory Test Results

Blood and urine will be collected at Screening, Baseline (blood only), Treatment Day 1 -T0 (urine only), Treatment Days 1, 2, 3, 4 and 5, at the Completion of the Last Infusion, and 24 hours Following the Completion of the Last Infusion (or Treatment Discontinuation date) for safety laboratory tests to be conducted at local laboratories. Safety assays include:

- Liver function tests (LFTs): Total bilirubin, alkaline phosphatase, alanine aminotransferase (ALT/SGPT), aspartate aminotransferase (AST/SGOT);
- Coagulation: Prothrombin time reported as the international normalized ratio (INR); and
- Urinalysis: dipstick plus microscopic evaluation of sediment if clinically indicated.

Any laboratory test result considered by the investigator to be clinically significant should be considered an AE.

If clinically significant abnormal laboratory values occur during the trial, the patient may be retested regularly until repeat test results return to normal, stabilize, or are no longer clinically significant.

Other Safety Assessments

Vital signs (blood pressure, temperature, heart rate, and respiration) will be measured at Screening, Baseline, Treatment Days 1, 2, 3, 4 and 5, at the Completion of the Last Infusion, and 24 hours Following the Completion of the Last Infusion inclusively. Height will be measured once (at Screening).

Physical examinations will be performed at Screening, Baseline, Treatment Days 1, 2, 3, 4 and 5, at the Completion of the Last Infusion, and 24 hours Following the Completion of the Last Infusion, inclusively (or Treatment Discontinuation Visit).

Single 12-lead ECGs will be performed at Screening, Baseline, Treatment Days 1, 2, 3, 4 and 5, at the Completion of the Last Infusion, and 24 hours Following the Completion of the Last Infusion, inclusively and will be evaluated locally according to usual site procedures.

Inter-current Illness and Pre-Existing Diseases

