11.6 Statistical Analyses

Tables and listings will be produced using SAS v9.2 or higher (SAS, Cary, NC). Data summaries by cohort group will be presented. For continuous variables, data will be summarized with the number of patients, mean, standard deviation, median, and minimum and maximum overall and by cohort. For categorical variables, data will be tabulated in frequency tables to display the number and proportion of patients for each category overall and by cohort. Baseline assessments for each outcome variable will be defined as the last measurement obtained before treatment initiation. Each point estimate will be presented with 2-sided 95% confidence intervals and all statistical tests will use a two-sided 5% significance level.

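### The ECG analysis plan names no heart-rate-corrected QT, does not count patients who cross the protocol's own QT limits, and leaves patients stopped before 72 hours out of the primary summary

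*Combined protocol and SAP*

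**What the plan says.** The memorandum at the end of the document states that no separate SAP was compiled, so Section 11 of the protocol is the analysis plan.

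- **Section 11.7.4**, individual and group data: "Means of the ECG intervals/durations will be listed for individual patients. Summary statistics, including mean absolute change from baseline", with the group data tabulated by cohort. No corrected interval, formula, time point, dose level or threshold count is named.
- **Section 11.6**, for continuous variables in general: "data will be summarized with the number of patients, mean, standard deviation, median, and minimum and maximum overall and by cohort".
- **Section 11.4**: the per-protocol set (at least 72 h of drug) is primary for all outcomes. The ITT set is a sensitivity analysis. A safety population is defined but not assigned to any analysis.
- **Section 6.3.4**: among the reasons for which treatment may be stopped is a prolongation of Qt/Qtc "of >60 msec over baseline", or a value above 500 msec. The entry criterion in Section 6.2.2 uses QT alone, with a 500 msec limit.
- **Section 9.8**: "Single 12-lead ECGs will be performed at Screening, Baseline" and at later visits, read locally.
- **Section 3.3.2**, on the earlier dose-ranging study: "There appeared to be a dose and exposure related increase in mean heart rate", starting at 10 g over 4 h, with modest QT effects to be interpreted cautiously.

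**The concern.** Safety is the primary objective, the 12-lead ECG is a named safety endpoint (Section 4.2.1), and the protocol treats repolarisation as a risk through its entry and discontinuation criteria. The analysis does not carry those criteria forward. Three features could each weaken a QT signal in the tables:

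1. QT shortens as heart rate rises. If the interval analysed is uncorrected, a mean change can look flat while corrected QT lengthens.
2. A mean dilutes a few large individual changes, and the by-cohort table pools all dose levels.
3. A patient whose infusion is stopped before 72 h because of QT prolongation is not in the primary set. Those most informative about the risk are the ones removed.

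In addition, a mean per patient is unclear when single ECGs are taken. If it means an average over visits, it dilutes a transient change further.

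**Working it through.** **Plan's own figures.** The documents give no ECG figure to reproduce. The related figure is enrolment: 36 evaluable with 25% non-evaluable gives 36 / 0.75 = 48, consistent with the planned maximum of 50. So up to 50 − 36 = 14 treated patients could lie outside the primary set. The synopsis attributes this to transplant, death or early discharge, not to QT.

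**Infusion rates.** Heart-rate rise reported from 10 g / 4 h = 2.5 g/h. Highest rate here: 20 g / 24 h = 0.83 g/h. Ratio 2.5 / 0.83 = 3.0. Dose levels pooled within a cohort run from 3.33 to 20 g/24 h, a sixfold range.

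**Masking by heart rate.** The documents give no QT or heart-rate values, so baseline QTcF of 420 msec and baseline heart rates of 70 to 100 bpm are assumptions. Fridericia: QTcF = QT / (60/HR)^(1/3). The QTcF rise that leaves QT unchanged is 420 × [((HR + Δ)/HR)^(1/3) − 1].

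Example, 80 to 100 bpm:
- QT at constant QTcF goes from 420 × (60/80)^(1/3) = 381.6 to 420 × (60/100)^(1/3) = 354.2, a fall of 27.4 msec.
- The masked rise is 420 × (1.25^(1/3) − 1) = 32.4 msec.

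| Baseline HR | +5 bpm | +10 bpm | +20 bpm |
|---|---|---|---|
| 70 | 9.8 | 19.1 | 36.7 |
| 80 | 8.6 | 16.8 | 32.4 |
| 90 | 7.6 | 15.0 | 29.1 |
| 100 | 6.9 | 13.6 | 26.3 |

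(Masked QTcF rise, msec.)

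**The formula matters.** In the same 80 to 100 bpm example with QTcF unchanged, Bazett's QTcB = QT / (60/HR)^(1/2) goes from 381.6 / 0.75^(1/2) = 440.6 to 354.2 / 0.6^(1/2) = 457.3, a rise of 16.7 msec. Uncorrected QT falls by 27.4 and QTcF does not change. At 100 bpm a QTcF of 501 msec is a QT of 501 × 0.6^(1/3) = 423 msec, so a 500 msec limit selects different patients depending on which interval is meant.

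**Dilution.**
- One patient at +61 msec, all others at 0: 61 / 18 = 3.4 msec in a cohort of about 18 (Section 5.1); 61 / 36 = 1.7 msec overall.
- One reading of +61 among a patient's 8 scheduled post-baseline ECGs (12, 24, 36, 48, 72 and 96 h, end of infusion, 24 h later): 61 / 8 = 7.6 msec.

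**What a count would show.** One of 18 above +60 msec is 5.6% (exact 95% CI 0.1% to 27.3%). Zero of 18 has an upper 95% limit of 18.5%.

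**The case against.** A reader might infer four stronger things that the documents do not support.

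- **That raw QT will be analysed.** Section 11.7.4 speaks only of intervals and durations, and Section 6.3.4 mentions Qtc. The gap is that no corrected interval or formula is specified.
- **That only means are reported.** Section 11.6 adds median, minimum and maximum, where an extreme could show. These do not say how many patients crossed a limit or at which dose, and it is not stated that they cover change or QTc.
- **That prolongation would be hidden from the trial.** Section 9.1.3 requires an adverse event for a treatment-emergent ECG finding, independent of an underlying condition, that needs intervention or leads to interruption or discontinuation. A new ECG finding with new symptoms should also be recorded. Section 11.7.1 tabulates events and withdrawals due to them, and the safety committee sees reasons for early withdrawal (11.5) and listings of patients with events of interest (9.7.1). But stopping under Section 6.3.4 is discretionary, so a symptom-free crossing without action need not be recorded under that ECG rule.
- **That the drug raises heart rate in this trial.** The mean rise was reported from about three times this trial's top rate, and Section 3.3.2 says 24-hour infusion avoids peak-concentration effects. A rise is plausible but not shown here: it was also linked to exposure, and tachycardia is listed as expected with both drug and disease (Section 9.1.2). A fall in heart rate would bias uncorrected QT the other way.

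It is also fair that this is a descriptive pilot, that early stoppers remain in the ITT sensitivity analysis, and that a per-patient mean over visits is possible, though not stated.

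**Conclusion.** The point holds for the ECG summary tables. Followed as written, Section 11.7.4 can dilute or mask a QT effect. It does not count patients who cross the protocol's own limits and stay on drug, and under Section 11.4 those stopped before 72 h are missing from the primary ECG summary.

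The dilution result (3.4 msec in a mean of 18) needs only the stated cohort size and a patient just over the limit. The heart-rate result (7 to 10, 14 to 19 and 26 to 37 msec for +5, +10 and +20 bpm) is conditional on heart rate rising, on QT being analysed uncorrected, and on the assumed baseline values. Adverse-event recording and minimum and maximum values limit the consequence: the signal could be lost in the table, not necessarily in the trial. The change should be made, because safety is the primary objective and the remedy is small.

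**What to change.** In Section 11.7.4:

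1. Name one correction formula in advance (for example Fridericia), using the heart rate from the same ECG. If that is not captured, use the nearest recorded pulse.
2. List individual interval values by time point instead of per-patient means.
3. Tabulate by cohort and dose level, in all treated patients, the number with QTc above 500 msec and the number with an increase of more than 60 msec, beside the mean change.

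Separately, the sponsor should reconcile the QT wording in Section 6.2.2 with the Qt/Qtc wording in Section 6.3.4. No clinical threshold is proposed; the counts use the protocol's own limits.

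Cost: revised wording and one extra table. The documents do not say that heart rate is recorded from the ECG. Vital signs are scheduled at the same visits, but the window of 3 h either side (Section 8.3) means pulse and ECG could be up to 6 h apart, so a pulse-based correction is second best. Counts or maxima from repeated single, locally read ECGs without a control arm are inflated by noise and should be read descriptively.
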